5.3.1 Haematology

Summary statistics of haematology observed values, change from baseline and percent change from baseline will be presented for all patients by parameter and visit.

In addition, a shift table showing the movement of patients with respect to CTC grade (according to NCI CTCAE v4.03) from baseline to each study visit will be presented by parameter. Patients will only be included in the missing category if they attended the respective post baseline visit but have no data available for that

parameter. Patients withdrawing prior to baseline will not be included in the missing category.

Individual patient haematology values will be plotted, with separate pages for each treatment group and parameter. Additionally, box plots will be produced to summarize values over time, with separate pages for each treatment group and parameter.

All haematology values will be listed showing reference ranges and flagging all abnormal findings and their clinical significance. Out of reference ranges will be flagged as high (H) or low (L).

5.3.2 Clinical Chemistry

Clinical chemistry data will be summarised and plotted in the same way as the haematology data.

All clinical chemistry values will be listed showing reference ranges and flagging all abnormal findings and their clinical significance. Out of reference ranges will be flagged as high (H) or low (L).

5.4 Vital Signs

Summary statistics of vital sign observed values and change from baseline from baseline will be presented by parameter and visit for all patients. For each parameter, the baseline value will be defined as the last scheduled or unscheduled value collected prior to the first dose of IMP. If the times of assessments have not been recorded, assessments carried out on the day of first IMP administration are considered to have taken place before IMP administration.

All vital sign data will be listed in full, flagging any unscheduled assessments.

5.5 Electrocardiogram (ECG)

All ECG data will be listed.

5.6 Physical Examination and ECOG Performance Status

The number and percentage of patients will be presented by ECOG performance status and study visit. In addition, a shift table presenting the shift from baseline in ECOG performance status by visit will be produced. The baseline value will be defined as the last scheduled or unscheduled value collected prior to first dose of IMP. Assessments carried out on the day of first IMP administration are considered to have taken place before the IMP administration, if the corresponding times have not been recorded. For post baseline, only data from scheduled visits will be included in the tables. Patients who attended a visit but have no ECOG data available will be included in the missing and total categories. Patients who withdrew prior to the visit will not be included in the summary for that visit and will be excluded from the denominator for calculation of percentages at that visit.

A listing will present ECOG assessment date and ECOG performance status together with whether a physical examination was performed and the date and time of examination.

6 EFFICACY EVALUATION

All efficacy evaluations will be performed on the efficacy and per protocol analysis sets unless specified otherwise.

6.1 Primary Immune Endpoints

A systemic immune response is defined as having a positive in vivo DTH and/or a positive in vitro T-cell response at least once during the study. Change in intra-tumoural T-cells in resected tumour tissue at surgery compared to pre-TG02-treatment core biopsy will be investigated.

The systemic immune responses are assessed by:

- TG02-specific DTH response. The DTH test is considered positive if erythema and/or induration are recorded as positive on the DTH response electronic case report form (eCRF) page.
- Presence of TG02 specific T-cells in peripheral blood. A patient is considered to have a positive T-cell response if the stimulation index (SI) is ≥ 2 .

The SI will be derived as follows:

$$\frac{\text{Mean (T cells + PBMC + TG02)}}{\text{Mean (T cells + PBMC (negative control))}}$$

For SI, mean is derived as the sum of the non-missing measurements divided by the number of non-missing measurements, rounded to the nearest whole number.

- Change in intra-tumoural lymphocytes in resected tumour tissue at surgery compared to pre-TG02-treatment core biopsy will be investigated.

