9. STUDY ASSESSMENTS

9.1. Assessment of Efficacy

9.1.1. Primary Efficacy Variables

A systemic immune response is defined as having a positive in vivo DTH and/or a positive in vitro T-cell response at least once during the treatment period. Change intra-tumoural T-cells in resected tumour tissue at surgery compared to pre TG02-treatment core biopsy will be investigated.

Delayed Type Hypersensitivity (DTH)

DTH tests are performed in order to demonstrate whether a TG02 RAS mutation specific immune response has been elicited.

[figure not shown]
Administration of TG02 only (without GM-CSF or preceded by TG02-treatment) must be injected intradermally in the lower area of the contralateral arm to TG02-treatment as a Delayed Type Hypersensitivity (DTH) test.

The DTH test is administered at baseline (Day 1 before treatment) week 4, week 6 and week 10 if surgery is scheduled after week 10 and the patient has not shown positive DTH reaction.

The DTH skin reaction assessment is to be performed 48 hours (+/- 4 hours) after each administration by the patient in a study specific diary. The patient will be instructed by the study nurse how to record the DTH response and how to enter the results into the diary. The DTH-test will be considered positive if the area of the skin reaction has an average diameter* of ≥ 5 mm at the 48 hours (+/- 4 hours) assessment ([Figure 4](#)).

Figure 4: DTH Skin Reaction Registration (induration and erythema)

* Average diameter: $\frac{a \text{ mm} + b \text{ mm}}{2}$

T-cell Analyses

Immunology-processed blood samples (PBMC) will be taken at baseline (Day 1, Week 1) and week 8 (Day 50). If surgery is after week 10, a third sample will be taken as close as possible up to the date of surgery. All samples will be processed and stored under appropriate conditions until being analysed in batches to minimize day to day assay variability. PBMCs will be analysed for the presence of TG02 specific T-cells which will be described in a study specific Immune Monitoring Plan.

Tumour biopsy assessment

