11.6.1.2. Immune Endpoints

Immune response

TG02-specific DTH immune response is defined as any positive DTH test during the course of the study. Number of patients with TG02-specific DTH response will be reported. Furthermore, the number of patients with TG02-specific DTH response by time point measurement will be reported.

Presence of TG02 specific T-cells:

Number of patients with TG02 specific T-cells at Day 1, Day 50 and, if applicable, at Day 64 (pre-surgery) will be reported.

Change in intra-tumoural lymphocytes (TILs):

The absolute count and relative change in TILs measured from tumour tissue collected prior TG02 treatment and from resected tumour will be presented in terms of descriptive statistics, as described in [section 11.4](#).

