6.1.1 TG02-specific DTH response

A TG02-specific DTH immune response is defined as any positive DTH test during the course of the study. A DTH-test will be considered positive if erythema and/or induration are recorded as positive on the DTH response assessment eCRF.

The number of positive DTH skin reactions (categorical variable) as well as the number and percentage of patients who have at least one positive DTH skin reactions will be presented by time point and overall.

All DTH assessment data will be listed in full.

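### A patient positive only at the Day 1 baseline test counts as a TG02 responder under the DTH and composite immune response definitions

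*SAP*

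**What the plan says.** Two responder rules are stated, each as any positive result within a window.

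- **DTH response.** SAP 6.1.1: "A TG02-specific DTH immune response is defined as any positive DTH test during the course of the study". Protocol 11.6.1.2 has the same rule: "TG02-specific DTH immune response is defined as any positive DTH test during the course of the study". For reporting, SAP 6.1.1 says that "patients who have at least one positive DTH skin reactions will be presented by time point and overall".
- **Composite systemic immune response.** SAP 6.1: "having a positive in vivo DTH and/or a positive in vitro T-cell response at least once during the study". Protocol 9.1.1 uses a different window, asking for a positive DTH and/or "a positive in vitro T-cell response at least once during the treatment period". For the T-cell part, SAP 6.1 sets positivity at a stimulation index of 2 or more at a single time point, with no comparison with the patient's own baseline.

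Protocol 6.4.2 schedules DTH on Days 1, 22, 36 and 50 (Day 64 under conditions) and PBMC sampling on Days 1 and 50 (with a later sample if surgery is after week 10). It calls both Day 1 assessments baseline.

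Protocol 9.1.1 says that the DTH test is done "in order to demonstrate whether a TG02 RAS mutation specific immune response has been elicited".

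**The concern.** A test labelled baseline should serve as the reference for a response, not as evidence of one. Here the Day 1 result can by itself make a patient a responder. For any given data, adding Day 1 can only raise the count or leave it unchanged, so the error has one direction.

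At stake is a primary-endpoint response rate on very few patients. With no hypothesis test (SAP 6.4.1), the descriptive count is itself the result. SAP section 4 sets Part I and Part II side by side, so one misclassified patient also affects how the two parts look against each other. The SAP defines baseline for laboratory values, vital signs and ECOG status (5.3, 5.4, 5.6) and uses change from baseline for intra-tumoural lymphocytes (6.1.3). It has no such rule for DTH or T-cell positivity.

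**Working it through.** The plan states no response rate or background positivity rate, so there is no figure to reproduce. The check sets the definitions against the schedule and then sizes the effect.

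**1. Does each window contain Day 1?**
- During the study: protocol 6.2 puts a patient on study from signed consent. Day 1 is inside.
- During the treatment period: protocol 6.4.2 starts that period on Day 1. Day 1 is inside.
- No section of either document limits response to later tests or requires conversion from negative.

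**2. Is the Day 1 result pre-treatment?**
- PBMC: yes. Table 6-1, footnote h, places the assessment before treatment.
- DTH: in part. The injection is given 30 minutes before the TG02-treatment (protocol 8.2) but read 48 hours (± 4) later (9.1.1), after the first dose. The protocol still calls it baseline.

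**3. Test cases**, for surgery at week 8.
- DTH positive on Day 1 and negative on Days 22, 36 and 50; stimulation index below 2 on Days 1 and 50. As written: DTH responder and composite responder. Counting only later tests: neither.
- Stimulation index of 2 or more on Day 1 only, every DTH negative. As written: composite responder. Counting only later tests: not.

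**4. Size per patient.** 1/4 = 25 points; 1/10 = 10 points. Four is the number treated so far (protocol 4.2) and ten is the Part II maximum. The actual sizes of the efficacy and per protocol sets are not given.

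**5. Chance of at least one such patient, for scale only.**

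Assumptions: background positivity per test q = 5% (range 2% to 10%); within-patient correlation r = 0.3; 58% true responders, all positive after Day 1. The 58% is the rate that protocol 4.1 cites for an earlier KRAS peptide vaccine in pancreatic cancer, so vaccine and tumour both differ. The documents give neither q nor r.

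Let p be a patient's own positivity rate, beta-distributed with a = q(1−r)/r = 0.1167 and b = (1−q)(1−r)/r = 2.2167. Then E[(1−p)^k] is the product over i = 0 to k−1 of (b+i)/(a+b+i).

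- Composite: 6 tests in all (4 DTH, 2 PBMC), 4 of them after Day 1. E[(1−p)^4] − E[(1−p)^6] = 0.8726 − 0.8429 = 0.0297. Times 0.42 for patients who are not true responders: d = 0.01247.
- At least one in n = 1 − (1−d)^n: **4.9% at n = 4 and 11.8% at n = 10**. With q from 2% to 10%: 2.2% to 8.3%, and 5.3% to 19.5%.
- With r = 0.6, d = 0.00497: 2.0% and 4.9%.
- DTH alone: 4 tests, 3 after Day 1. E[(1−p)^3] − E[(1−p)^4] = 0.8921 − 0.8726 = 0.0195. The 58% counts DTH and/or T-cell proliferation, so it is at best an upper figure for DTH. Using it gives d = 0.0082 (3.2% and 7.9%); with no true responders d = 0.0195 (7.6% and 17.9%). A smaller DTH responder share falls between these.
- Extreme bound for the composite, with independent tests and no vaccine effect: d = 0.95^4 − 0.95^6 = 0.8145 − 0.7351 = 0.0794, giving 28.2% and 56.3%.

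**The case against.** The strongest reply is that this is a wording gap with little practical reach. Results are shown by time point with Day 1 separate, and all are listed, so in at most 16 patients a Day-1-only positive can be found by eye. Genuine pre-existing reactivity would tend to persist, and such a patient is a responder under either rule. The table shells (SAP section 1) are a separate document, and the T-cell analysis is one "which will be described in a study specific Immune Monitoring Plan"; either might contain a restriction. Much of this stands, and it limits the size. It does not change the definitions, which both documents state without reference to any such restriction.

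Several stronger readings are tempting but unsupported:

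- **That a Day 1 DTH positive is a purely pre-treatment finding.** The reading follows the first dose. Only the blood sample is fully pre-treatment.
- **That a composite rate is known to be tabulated.** SAP 4.2 has an output row labelled Immune Response next to a separate DTH row, which makes a composite table plausible. But it is only a row label, and under protocol 11.6.1.2 the same words head the DTH definition.
- **That the T-cell overall row is certainly inflated.** SAP 6.1.2 does not define overall, SAP 6.2.3 uses the same phrase for continuous SUV data, and protocol 11.6.1.2 asks for T-cell counts by visit only: "Number of patients with TG02 specific T-cells at Day 1, Day 50 and, if applicable, at Day 64 (pre-surgery) will be reported".
- **That the decision to open Part II would change.** Protocol 7.2 ties it to the level of immune activation, but no numerical threshold exists.
- **That a misclassified patient is more likely than not.** The 56% figure needs fully independent tests and a vaccine with no effect.

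**Conclusion.** The point holds and should be fixed. It follows from the text alone that a patient positive only on Day 1 is a responder under a stated primary-endpoint rule. The clearly affected output is the overall DTH responder count. The composite is affected wherever it is tabulated, and the T-cell overall row only if overall means any time point.

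The 25-point and 10-point shifts are arithmetic for denominators of 4 and 10. The probabilities of about 5% and 12% rest wholly on assumed background positivity, correlation and responder share, and fall with stronger correlation. False positives at later visits are a separate matter that this change would not touch.

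**What to change.** In SAP 6.1, 6.1.1 and 6.1.2, count toward response only DTH and PBMC tests given after the first TG02-treatment: DTH from Day 22, T-cell from Day 50. Define overall in 6.1.1 and 6.1.2 the same way, and record the change in SAP 3.5. Report Day 1 positives in a separate baseline row, and flag responders already positive on Day 1 so that persisting or boosted reactivity is not read as newly induced.

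One dependency needs attention. The protocol synopsis and sections 6.4.2 and 9.1.1 make the week 10 DTH depend on earlier DTH tests having been negative. Footnote 4 to Figures 2 and 3, Table 6-1 footnote i and the Table 8-1 footnote look only at the week 8 result. Under the first reading, a Day 1 positive could cost a patient the week 10 test, and excluding Day 1 would then leave that patient with fewer chances to respond. These passages must be reconciled, and any Day-1-positive patient who missed the week 10 DTH for that reason should be flagged in the responder table.

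Cost: a clause in three SAP sections, one entry in 3.5, one changed derivation, one table row and the flags. It needs no new data collection, although a week 10 test already missed cannot be recovered. The reported response rate may be lower.

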6.1.1 TG02-specific DTH response

A TG02-specific DTH immune response is defined as any positive DTH test during the course of the study. A DTH-test will be considered positive if erythema and/or induration are recorded as positive on the DTH response assessment eCRF.

The number of positive DTH skin reactions (categorical variable) as well as the number and percentage of patients who have at least one positive DTH skin reactions will be presented by time point and overall.

All DTH assessment data will be listed in full.

6.1.2 Presence of TG02-specific T-cells

Immunology-processed blood samples for peripheral blood mononuclear cells (PBMC) will be drawn at baseline and week 8 (Day 50). If surgery is after week 10, a third sample will be drawn as close as possible to the date of surgery. PBMCs will be analysed for the presence of TG02-specific T-cells. Summary statistics of patients with TG02-specific T-cells will be presented by time point and overall.

All PBMC and TG02-specific T-cell data will be listed.

6.1.3 Change in intra-tumoural lymphocytes

Tumour samples will be taken pre TG02-treatment in the form of a study specific biopsy and at the time of surgery in the form of resected tumour tissue (the post treatment sample). If for any reason a patient does not proceed to surgery, a biopsy will be obtained at the time of planned surgery if possible. Summary statistics of intra-tumoural lymphocytes observed values and change from baseline will be presented.

All intra-tumoural lymphocyte data will be listed.

6.2 Secondary Efficacy Variables

6.2.1 Immune suppression factors in tumour specimens

Immune suppression factors (such as PD-L1, Treg and MDSC) will be summarised in the same way as the intra-tumoural lymphocyte data.

All PD-L1, Treg and MDSC data will be listed.

6.2.2 Pathological responses and markers of apoptosis in tumour specimens

Pathological response and markers for apoptosis (such as Granzyme B, Cleaved caspase-3) data will be summarised in the same way as the intra-tumoural lymphocyte data.

All pathological response data will be listed.

6.2.3 Change in standard uptake values assessed by FDG PET-CT

FDG uptake reflects the tumour activity independent of the morphologic characteristics. FDG PET-CT images will be obtained at screening and as close as possible up to the date of surgery. Standard uptake value (SUV) at baseline and post treatment will be assessed.

Summary statistics of SUV observed values and change from baseline will be presented by time point and overall for all patients.

All FDG PET-CT examination and assessment data will be listed.

6.2.4 Non-Target Lesions

Non-target lesion data will be listed in full.

6.2.5 Change in CEA

Tumour marker assessment will take place at screening and week 8 and if surgery is after week 10, a sample will be taken as close to possible to surgery. Summary statistics of observed values of CEA, change from baseline and percent change from baseline will be presented by time point for all patients.

All CEA data will be presented in the listings.

6.3 Exploratory Efficacy Variables

6.3.1 Change in ctDNA

Change in ctDNA will be measured to follow the levels of ctDNA during the treatment period. Summary statistics of observed individual values of ctDNA, mean of the observed results together with fold change from baseline will be reported by time point for all patients.

If only one result is available, no mean will be calculated, and this value will be used to produce the fold change from baseline.

All ctDNA data will be listed.

The above will be repeated for cytokines.

6.3.2 Functionality of RAS mutation specific T cells in tumour tissue and peripheral blood

The reporting of the functionality of RAS mutation specific T cells in tumour tissue and peripheral blood will be reported separately per patient and included as an appendix to the study report.

6.4 Statistical Analysis

6.4.1 Hypotheses to be Tested

No statistical hypothesis is defined, only descriptive statistics will be produced.

6.4.2 Handling of Dropouts or Missing Data

In general, the denominator for percentage calculations will be the number of patients in the analysis set. However, unless specified otherwise, for tables by time points the percentages and summary statistics will be calculated using the number of patients with available data at that time point.

6.4.3 Interim Analyses and Data Monitoring

No interim analysis is planned for this study.
